8.5 Methods of Endpoint Assessment

The **primary endpoint (safety measure)** of this Clinical Investigation will be assessed as follows:

- The correlation of a serious adverse event with the 8-Plate Plus will be freely determined by the Investigator according to the following options: not related / possibly related / definitely related. Serious events assessed as possibly or definitely related to the 8-Plate Plus will be included in the safety measure calculation.
- It is understood that, for serious events judged as possibly or definitely related to the 8-Plate Plus, the Sponsor reserves the right to supplement the Investigator's assessment with the opinion of an independent orthopaedic surgeon. If the independent orthopaedic surgeon subsequently identifies a surgical technique error in the primary implantation, in agreement with the Investigator, the event initially classified as possibly or definitely related to the 8-Plate Plus may be reclassified as not related and, consequently, excluded from the safety measure calculation. Similarly, serious adverse events due to use not compliant with the manufacturer's Instructions for Use (off-label use) will be excluded from the safety measure calculation.

The **secondary endpoints (benefit measures)** of this Clinical Investigation, as described above, will be assessed by comparing, for each patient, the preoperative radiographs (untreated deformity) with the radiographs collected at the plate removal visit (Visit 4).

The data related to the primary and secondary endpoints, already available in the patients' medical records, will be:

- entered into the validated electronic database provided free of charge by the Sponsor to each Investigator for data collection within the Clinical Investigation;
- analysed using descriptive and/or quantitative statistics and presented with the corresponding confidence intervals (for further details, see the *Statistics* section of this Clinical Investigation Plan).

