1 SYNOPSIS

TITLE	Retrospective post-market Clinical Investigation for the evaluation of the safety and clinical benefit of Guided Growth Plate System Plus (Orthofix Srl) medical device for the treatment of lower limb bone deformities of the in growing children.
INVESTIGATIONAL DEVICE DESCRIPTION	The GGPSP consists of different sizes of eight-Plate and quad-Plate designed to accept cannulated or solid screws available in a variety of sizes. Plates and screws are available in sterile or non-sterile configuration. The device is designed for the gradual correction of pediatric congenital as well as acquired bone deformities in long bones, provided that the physis (growth plates) are not fused. The plates feature a contoured waist and low profile for pediatric usage. There is a center hole in the plates for a temporary guide pin to be implanted to aid application and removal of the plate. The plates are fixed to the bone over the growth plate by screws. These screws are not locked to the plate, but rather are allowed to swivel and diverge in their position as bone growth occurs. The implant acts like a flexible hinge, halting on one side (hemiepiphysiodesis) or on both sides (epiphysiodesis) the growth plate and thus guiding bone growth. Application and removal of the GGPSP can be performed with Orthofix general orthopaedic instrumentation.
OBJECTIVES AND ENDPOINTS	
Primary objective: evaluate the safety profile of GGPSP.
 
Primary endpoint: percentage of subjects that encountered at least one complication, to be intended as:
 
 · an expected or unexpected serious adverse effect related to the device; · an hardware failure (i.e. breaking, loosening or bending of the plate or of the screws) during follow-up period (from time of plate application to the first post-removal visit). 
Secondary objective: evaluate the clinical benefit of treatment with the GGPSP.
 
Secondary endpoint: percentage of subjects that achieved the treatment goal as defined below:
 
 · for hemiepiphysiodesis, femur and/or tibia angular deformity partially or completely corrected to standard alignment (mMPTA and mLDA between 85° and 89°); · for epiphysiodesis, femur and/or tibia length discrepancy partially or completely corrected to the matching length of the contralateral morphologically normal limb during follow-up period (from time of plate application to the first post-removal visit).

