2.3 Detailed Device Description

The 8-Plate Plus system consists of plates of various sizes and shapes designed to accommodate cannulated or solid screws available in different lengths (Fig. 1). The plate with two holes for the fixation screws, which is also the most commonly used, is referred to as the “8-Plate” due to its shape and gives the name to the entire system. A version of the plate with four holes for fixation screws is also available and, due to its shape, is referred to as the “Quad-Plate” (Fig. 1).

Product Code Description

Implants	
	Description
eight-Plate	Color Coded eight-Plate Plus - Green 12mm Color Coded eight-Plate Plus - Blue 16mm Color Coded eight-Plate Plus - Purple 20mm
quad-Plate	Color Coded quad-Plate Plus - Blue 16mm Color Coded quad-Plate Plus - Purple 22mm

Ø3.5 Solid Screw eight-Plate Plus Color Coded - Yellow
Ø4.5 Solid Screw eight-Plate Plus Color Coded - Blue
Ø4.5 Cannulated Screw eight-Plate Plus Color Coded - Green

Figure 1: Examples of plates (“8-Plate” on the left and “Quad-Plate” on the right) and screws from the 8-Plate Plus system.

The plates feature a contoured waist and low profile, making them suitable for paediatric use. Each plate includes a central hole for the insertion of a temporary guide wire, intended to facilitate both the application and removal of the plate.

The plates are secured to the bone across the growth plate using screws (Fig. 2).

Figure 2: Implantation of 8-Plate (left) and Quad-Plate (right) for hemi-epiphysiodesis.

These screws are not locked to the plate but can instead rotate and diverge under the pressure exerted by the growth plate. The implant functions as a flexible hinge (Fig. 3), inhibiting the growth plate on one side (hemi-epiphysiodesis) or on both sides (epiphysiodesis), thereby guiding bone growth.

[figure not shown]

Figure 3: “Hinge-like” configuration of the implant.

The positioning of the screws is monitored over time by radiographic imaging, and the implant is always removed before the screws reach their maximum angle of divergence. The system thus exerts pressure that temporarily inhibits growth of the growth plate.

[figure not shown]

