2.4 Surgical Procedure Related to the Use of the Medical Device

Below is a brief description of the main steps for the application and removal of the 8-Plate Plus. For more detailed information regarding the surgical steps, please refer to the surgical technique guide available at: <https://abs.orthofix.it/db/resources/EP-1701-OPT-E0.pdf>

Surgical Procedure:

1. Using a radiopaque instrument and a fluoroscope, identify the physis in the anatomical area where the plate and screws will be applied according to the desired correction. Mark the skin at the level of the physis and make a 1–2 cm incision.
2. Once the bone is exposed, insert the guide wire through the central hole of the plate and into the physis using a power drill, to a depth generally not exceeding 1 cm. Then confirm correct positioning of the guide wire with fluoroscopy.
3. Select the most appropriate plate size based on the patient's anatomy and the intended application. Before inserting the screws, ensure the plate is properly seated against the bone. The plate has a standard base curvature of 10°, but it can be bent an additional 10° if needed to ensure proper bone contact.
4. Plate fixation is performed using the dedicated instrumentation, following these main steps:
 - Insertion of epiphyseal and metaphyseal guide wires;
 - Selection of the screws and the corresponding cannulated drill bits;
 - Pre-drilling of the epiphyseal hole followed by the metaphyseal hole;
 - Assembly of the screwdriver and insertion of the screws;
 - Removal of the guide wires;
 - Wound closure with sutures.

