8.4 Endpoints

In this Clinical Investigation, the two variables selected as the primary and secondary endpoints, intended to measure the primary and secondary objectives of the Investigation respectively, also correspond to the treatment response measures routinely used in the standard clinical practice of the participating Centre, namely:

- **Primary endpoint (safety measure):**

The safety of the 8-Plate Plus will be assessed by the percentage of subjects who, during the observation period — i.e., from plate implantation to the first follow-up visit after plate removal — experienced at least one complication certainly or potentially related to the investigational device. Such complications are defined as:

- a Serious Adverse Device Effect (SADE), expected or unexpected;
- a hardware failure (e.g., breakage, detachment, or bending of the plate or screws).

- **Secondary endpoint (benefit measure):**

The clinical benefit of treatment with the 8-Plate Plus will be assessed by the percentage of subjects who, during the observation period — i.e., from plate implantation to the first follow-up visit after plate removal — achieved the treatment objective, defined as:

- for hemiepiphysiodesis: partial or complete correction of the angular deformity of the femur and/or tibia towards the standard alignment direction (mMPTA and mL DFA between 85° and 89°);
- for epiphysiodesis: partial or complete correction of femoral and/or tibial length discrepancy in relation to the morphologically normal contralateral limb length.

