8.10 Medical-Surgical Procedures and Clinical Investigation Follow-up

The Investigator will include in the study those patients who, at the selection visit (Visit 0), meet all eligibility criteria. It is understood that, given the retrospective nature of the study and considering that the consent of eligible patients was obtained a priori, patients will not attend the selection visit nor any subsequent visits. Furthermore, during the selection visit (Visit 0), the Investigator will collect the patient's demographic data and medical history.

The data to be collected are as follows:

- Demographics and BMI
- Medical history
- Indication(s) treated
- Deformity parameters:
 - hip-knee-ankle angle (HKA)
 - anatomical lateral distal femoral angle (aLDFA)
 - mechanical axis deviation (MAD)
 - mechanical lateral distal femoral angle (mLDFA)
 - mechanical medial proximal tibial angle (mMPTA)
 - lateral distal tibial angle (LDTA)
 - fibular station
 - femur, tibia, fibula length
 - tibia-to-fibula ratio
 - femur-to-tibia ratio

Subsequently, data of interest related to the surgery for plate implantation (Visit 1) and to the treatment period — i.e., the two postoperative follow-up visits (Visits 2 and 3) up to plate removal (Visit 4) — will be collected. In particular, the following data will be gathered:

- Age at surgery
- Surgical details (duration, complications, postoperative X-ray) and data related to the implanted device(s) (i.e., quantity, type, and size)
- Concomitant medications and treatments
- Achievement of the treatment objective
- Treatment duration (calculated from implantation to removal)
- Complications (both device-related and non-device-related, leading or not to premature removal or unplanned surgery).

The course of treatment will be monitored as per routine clinical practice, and data corresponding to the follow-up visit, scheduled on average 4 months after plate removal (Visit 5), will be collected. At the follow-up visit, the following additional information will be recorded:

[figure not shown]
- Concomitant medications and treatments relevant to the study
- Status of the corrected deformity
- Deformity rebound
- Complications/Adverse events occurring after plate removal.

The Clinical Investigation data will be recorded in the patient's medical record and entered into a validated electronic data capture system provided by Orthofix Srl.

Note:

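### Hardware failure is one of the two primary-endpoint components, but 8.5 gives no way to identify it, so failures seen on film or at removal and never noted can go uncounted

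*Combined protocol and SAP*

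**What the plan says.** **Endpoint (8.4).** A subject counts if, between implantation and the first visit after plate removal, there was either "a Serious Adverse Device Effect (SADE), expected or unexpected" or "a hardware failure (e.g., breakage, detachment, or bending of the plate or screws". Only the first component carries a seriousness condition.

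**Definition in the synopsis.** The second component reads "an hardware failure (i.e. breaking, loosening or bending of the plate or of the screws". This is a closed list with loosening in it. Section 8.4 gives an open list with detachment in that place.

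**Assessment (8.5).** The rules for the primary endpoint cover relatedness of serious events, optional independent review, and exclusions for technique error and off-label use. The inclusion rule is "Serious events assessed as possibly or definitely related to the 8-Plate Plus will be included in the safety measure calculation". Hardware failure is not mentioned. Radiographs appear only for the benefit endpoint, which compares "the preoperative radiographs (untreated deformity) with the radiographs collected at the plate removal visit (Visit 4").

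**Data collected (8.10 and 8.12).** The list in 8.10 includes "Surgical details (duration, complications, postoperative X-ray") and an item for all complications, device-related or not. In table 8.12 the X-ray row is marked at Visits 0 and 4 only, and the safety row at Visits 1 to 5. The content of the safety row is not defined.

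**Device background (2.3, 2.4).** In device use, "The positioning of the screws is monitored over time by radiographic imaging". The screws are meant to diverge as the bone grows. At implantation the plate has a base curvature, and "it can be bent an additional 10° if needed to ensure proper bone contact".

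**The concern.** The primary rate is built from charts. For serious events, 8.5 tells the investigator what to judge and how. For hardware failure it names no source, no criterion and no reference image, and it does not say who judges relatedness or whether the technique-error and off-label exclusions apply.

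A bent plate or loosened screw that caused no symptoms therefore enters the rate only if someone recorded it as a complication at the time. Omissions of that kind lower the observed rate, and this is the rate that section 16 sets against the published range of 3% to 12%.

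The definition needs care for a second reason. Some bending is done on purpose at implantation, so bending seen on a later film means little without the postoperative film beside it. Section 8.10 lists that film but table 8.12 does not mark it. The two wordings of hardware failure also leave it open whether a loosened screw that has not detached counts.

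**Working it through.** **1. Which records can reveal a hardware failure, and does the plan direct anyone to them?**

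| Record | In the plan | Used for hardware failure? |
|---|---|---|
| Complication written in the notes | 8.10 complications item; safety row of 8.12, Visits 1 to 5 | Yes, in effect |
| Preoperative film (Visit 0) | 8.5, 8.12 | Cannot help: no implant present |
| Postoperative film | Listed in 8.10, not marked in 8.12 | No role stated |
| In-treatment films | Suggested by 2.3; not marked in 8.12 | No role stated |
| Film at removal (Visit 4) | 8.5, 8.12 | Benefit endpoint only |
| Removal operation | Visit 4 | No instruction to record hardware status |

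The gap is therefore failures visible on a film or at removal that nobody wrote down as a complication.

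**2. The plan's own figure.** Inputs from 8.7 and 16: 70 implants, 3% expected, two-sided 95% exact binomial interval, stated upper limit 9.94%, reference 12%.

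- Expected events: 0.03 × 70 = 2.1, rounded to 2.
- Clopper-Pearson upper limit: U = the 0.975 quantile of Beta(x + 1, n − x).
- x = 2, n = 70: the 0.975 quantile of Beta(3, 68) is 9.94%. The stated figure is reproduced.

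**3. Effect of one event, found or missed.**

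| Events / n | Observed rate | Upper limit |
|---|---|---|
| 2/70 | 2.86% | 9.94% |
| 3/70 | 4.29% | 12.02% |
| 0/40 | 0% | 8.81% |
| 1/40 | 2.50% | 13.16% |

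On the plan's basis, two counted events is the most that keeps the limit below 12%. The rows for 40 use the approximate number of patients.

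**4. Illustration under assumptions.** The documents give neither the share of endpoint events that are hardware failures nor the fraction of those that the notes would capture. Assume that half of the events are hardware failures, that a fraction s of them is captured, and that implants are independent. The counted rate is then p × (0.5 + 0.5s); for example, 6% × (0.5 + 0.5 × 0.5) = 4.5%. The chance of two or fewer counted events in 70 is:

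| True rate p | s = 100% | s = 75% | s = 50% |
|---|---|---|---|
| 3% | 0.65 | 0.72 | 0.79 |
| 6% | 0.20 | 0.28 | 0.39 |
| 12% | 0.01 | 0.02 | 0.04 |

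Under these assumptions, incomplete capture makes an upper limit below 12% moderately more likely at 3% and 6%. At a true rate of 12% that outcome stays unlikely.

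**The case against.** The strongest reply is that 8.5 is not the only route into the database. Complications of every kind are collected, safety is recorded at Visits 1 to 5, section 15 has all adverse events and device effects reported, and section 9 has endpoint variables monitored and entries checked against source data. Every included patient has had the plate removed (8.6.1), so the surgeon saw the hardware directly, and a broken, bent or detached part would normally still be evident. This stands and narrows the point. What remains is that no text tells the abstractor to take hardware status from the removal note or a film when it was not called a complication.

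Several stronger readings are tempting, and the documents do not support them:

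- *Non-serious hardware failures are excluded.* Section 8.4 lists them without a seriousness condition. Section 8.5 is silent, which is an ambiguity and not an exclusion.
- *Half of the endpoint is unmeasured.* Hardware failure is one of two listed components; its share of events is unknown.
- *A Visit 4 film is useless because it cannot date the change.* The endpoint is yes or no per subject over the whole period, so timing does not matter.
- *In-treatment films exist for every patient.* That is inferred from a general statement in 2.3. Section 8.11 warns that some visits may not apply, and the X-ray row of 8.12 may simply mark the benefit films, since it matches the benefit row.
- *The literature comparison is biased towards the device.* Missed failures lower the study rate, but the documents do not say how the 3% to 12% was ascertained, and intended bending scored as failure would push the other way.

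The jump from 0/40 to 1/40 also owes much to a separate matter: the endpoint counts subjects, while the sample size counts implants. The 70-implant figures are the fairer measure here.

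**Conclusion.** The point holds in a limited form. One of the two primary-endpoint components has no assessment rule, its definition differs between the synopsis and 8.4, and table 8.12 disagrees with 8.10 on the postoperative film. Followed as written, the plan can miss hardware failures that were visible but never noted as complications, and each omission lowers the primary rate.

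The number of such omissions cannot be estimated from the documents. One is enough to matter: it separates an upper limit of 12.02% from one of 9.94% on the plan's basis. The crossing of 12% is narrow, and section 16 describes a descriptive analysis with no pass or fail rule, so the consequence is a change in how the result reads and not a failed test. These limits treat the 70 implants as independent, as the plan's own calculation does.

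This should be settled before data abstraction begins. A reader might infer that every plate and screw has to be graded on every film; the gap does not call for that much.

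**What to change.** In 8.5:

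- State that hardware failure counts whether or not it is serious.
- Use one definition throughout, reconciling loosening in the synopsis with detachment in 8.4.
- Require one hardware-status entry per implant (intact / bent / broken / loosened or detached), taken from the Visit 4 film, the removal operation note and any in-treatment films on file. Use the postoperative film as reference, so that bending done at implantation is not scored as failure.

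In table 8.12, mark the postoperative X-ray to agree with 8.10, and mark in-treatment films as where on file. In the report, give the number of subjects with at least one in-treatment film.

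Cost: wording in two sections, one eCRF entry per implant, and some extra abstraction time for about 40 charts. The rate may come out less favourable. No new imaging or extra reader is needed. The entry draws only on records already gathered in routine care, which appears consistent with the limit on data in 5.1; the sponsor should confirm that when making the change.

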SAMPLE SIZE CALCULATION	
For the aim of the sample size calculation, the safety profile of GGPSP will be compared to safety data reported in the scientific literature for the treatment of lower limb deformities by the means of guided growth performed by tension band plate. The sample size, therefore, was calculated estimating the required number of subjects so that the primary endpoint of the Study for GGPSP (i.e. percentage of subjects that experienced at least one complication as above described) ranges within the state-of-art safety profile of this treatment, that is, it is within the safety data reported in the literature for its previous version (the GGS) and for equivalent medical devices. Specifically, the scientific literature reports that the percentage of patients treated by a tension band plate for a lower limb deformity that faced at least one complication is between 3% and 12% depending on the many factors, mainly the diversity of the primary diagnosis. Assuming the expected percentage of patients with at least one complication for GGPSP will be 3%, 70 implants was calculated to be the sample size of this study so that the upper limit of the 95% confidence interval for the primary endpoint, based on the exact binomial method, is under 12%. Since each patient may have been treated for the correction of multiple localized deformities in different long bones, it is understood that each eligible subject may contribute to the data collection of multiple implants (average 2). For this reason, approximately 40 patients are expected to be enrolled.

2 Medical Device Information

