8.7 Number of Patients Expected to be Enrolled

The sample size was therefore calculated by estimating the number of implants required so that the confidence limits of the study's primary endpoint for the 8-Plate Plus (i.e., the percentage of subjects who experienced at least one complication certainly or possibly related to the investigational device, as described above) fall within the safety profile of the state of the art for this treatment, namely within the safety data reported in the literature for its predecessor (the GGS) and for other equivalent medical devices.

Specifically, the scientific literature reports that the percentage of patients treated with a tension band plate for a lower limb deformity who experienced at least one device-related complication ranges from 3% to 12%, depending on several factors, primarily the heterogeneity of the primary diagnosis [7].

Assuming that the expected percentage of patients with at least one complication certainly or possibly related to the device for the 8-Plate Plus will be 3%, the sample size calculation showed that, in order for the upper limit of the 95% confidence interval for the primary endpoint (calculated using the exact binomial method) to remain below 12% (i.e., 9.94%), 70 implants are required.

As each patient may have been treated for the correction of multiple deformities located in different long bones, it is understood that each eligible subject may contribute data for more than one implant (on average 2). For this reason, approximately 40 patients are expected to be enrolled.

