- revise the Clinical Investigation Plan and any study documentation impacted by the amendments, ensuring that all changes are appropriately tracked;
- in the case of non-substantial amendments, promptly notify in writing the participating Site and the corresponding Ethics Committee for information purposes, providing copies of the revised documents;
- in the case of substantial amendments, suspend the Clinical Investigation until a new favourable opinion has been issued by the relevant Ethics Committee.

15 Adverse events

The foreseeable adverse events related to the use of the 8-Plate Plus, as identified through the risk analysis performed during product design, are described in the section “POSSIBLE ADVERSE EFFECTS” of the device’s Instructions for Use (http://abs.orthofix.it/db/resources/PQ_EPP.pdf).

This Clinical Investigation is a retrospective observational study and, therefore, does not pose additional risks to patients or Investigators.

Definitions:

- An *adverse event (AE)* is any undesirable experience associated with the use of the device in a patient.
- An *adverse event* is defined as a *serious adverse event (SAE)* when, as a consequence of such event, the patient:
 - dies;
 - experiences a life-threatening event;
 - requires prolongation of hospitalisation;
 - requires re-hospitalisation;
 - suffers permanent disability;
 - experiences a congenital anomaly or birth defect.

Expected Serious Adverse Device Effects (SADEs) — i.e., those already reported in the device Instructions for Use — are further classified as **E(SADE)** (*Expected SADE*). Conversely, Serious Adverse Device Effects not previously reported in the device Instructions for Use are further classified as **U(SADE)** (*Unexpected SADE*).

All adverse events and adverse device effects associated with the use of the device that occurred during the entire observation period of the Clinical Investigation will be classified and reported to the Sponsor via the electronic database provided by the Sponsor.

Since this is a retrospective Clinical Investigation, serious adverse events (SAEs), having already followed the reporting procedures of the vigilance system, are not subject to prompt notification upon awareness, as otherwise required by GCP (Section 4.11.1).

16 Statistics

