The safety profile of the 8-Plate Plus, as measured in the present Clinical Investigation, will be compared with the safety data reported in the scientific literature for the treatment of lower limb deformities by guided growth performed with equivalent tension-band plates.

The sample size calculation was performed in order to estimate the confidence intervals for the primary endpoint (safety outcome related to treatment response) of the 8-Plate Plus and to enable a reliable comparison with the data reported in the literature.

Accordingly, the sample size was determined by estimating the number of implants required so that the confidence intervals for the study primary endpoint with the 8-Plate Plus would fall within the established safety profile for this treatment, namely within the range of safety data reported in the literature for its predecessor (the GGS) and for equivalent medical devices.

Specifically, the scientific literature indicates that the proportion of patients treated with a tension-band plate for lower limb deformity who experience at least one device-related complication ranges between 3% and 12%, depending mainly on the heterogeneity of the underlying diagnosis.

Assuming that the expected proportion of patients experiencing at least one complication with the 8-Plate Plus is 3%, the sample size calculation showed that, in order for the upper limit of the 95% confidence interval for the primary endpoint (calculated using the exact binomial method) to remain below 12% (i.e., 9.94%), a total of 70 implants (in approximately 40 patients) are required.

The clinical data collected during the present Clinical Investigation will be analysed using descriptive statistics:

- the primary endpoint will be presented as a percentage value with its corresponding 95% confidence interval;
- the secondary endpoint will be presented as a percentage value with its corresponding 95% confidence interval.

The clinical data obtained from this Clinical Investigation will be used to complete the evaluation of the clinical performance and safety of the 8-Plate Plus, with the objective of confirming that the device can be considered safe and effective as hypothesised during its development, based on the preclinical evaluations conducted for CE marking.

17 Publication of Results

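### The causality review and off-label rule in Section 8.5 can only take serious events out of the primary safety rate, and the rate before removals is not planned for reporting

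*Combined protocol and SAP*

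**What the plan says.** Section 8.4 defines the primary endpoint as the percentage of subjects with at least one complication certainly or potentially related to the device: a serious adverse device effect or a hardware failure.

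Section 8.5 sets out how serious events enter the count. The Investigator rates each as not, possibly or definitely related, and the last two categories count. Two rules then act on that count:

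- **Second opinion.** "for serious events judged as possibly or definitely related to the 8-Plate Plus, the Sponsor reserves the right to supplement" the Investigator's view with that of an independent orthopaedic surgeon. If the surgeon identifies a technique error at the primary implantation and the Investigator agrees, the event "may be reclassified as not related and, consequently, excluded from the safety measure calculation".
- **Off-label use.** Serious events due to use that does not comply with the manufacturer's "Instructions for Use (off-label use) will be excluded from the safety measure calculation".

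On data capture, Section 8.10 collects "Complications (both device-related and non-device-related, leading or not to premature removal or unplanned surgery", and Section 15 says that all adverse events and device effects "will be classified and reported to the Sponsor via the electronic database provided by the Sponsor". On reporting, Section 16 says only that "the primary endpoint will be presented as a percentage value with its corresponding 95% confidence interval".

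The yardstick is a literature range. Section 8.7 gives it as the percentage of patients "who experienced at least one device-related complication ranges from 3% to 12" percent. The synopsis gives it as the percentage "that faced at least one complication is between 3% and 12" percent, without the device-related qualifier.

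**The concern.** Both rules act only on serious events that would otherwise count, and removal is the only outcome described. No section provides for review of a serious event rated not related. A classification error that favours the device therefore stays, while one that goes against it can be corrected. The review is optional, the Sponsor starts it, and no criteria say which events are sent.

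The plan also does not let a reader see what the rules did. The result will be set against a 3% to 12% literature range, and the documents do not say whether technique-error or off-label events were removed from that range. If they were not, the comparison leans towards the device, and a single post-removal percentage would not show by how much. With one or two expected events, one removal can decide which side of 12% the upper limit falls on.

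**Working it through.** **1. Direction of each step in Section 8.5**

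| Investigator's rating of a serious event | Further step | Possible effect on the count |
|---|---|---|
| Not related | None | None |
| Possibly or definitely related | Optional independent opinion | Unchanged or lower |
| Due to off-label use | Excluded | Unchanged or lower |

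No row can raise the count. Hardware failures are a separate component in Section 8.4, and the removal text does not name them.

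**2. Reporting commitments**

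Sections 8.10 and 15 capture all events. Section 16 plans one percentage with its interval. Section 17 promises a final report of aggregated data. None specifies a rate before removals, a list of removed events or a sensitivity analysis.

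**3. The plan's own figure**

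Inputs from Sections 8.7 and 16: expected rate 3%, 70 implants in about 40 patients, exact binomial 95% interval, upper limit to stay below 12%, stated value 9.94%.

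The exact upper limit for x events in n units is the 0.975 quantile of Beta(x + 1, n − x). Expected events: 0.03 × 70 = 2.1, rounded to 2. The 0.975 quantile of Beta(3, 68) is 9.94%, which reproduces the stated value.

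**4. Effect of one removal**

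The endpoint is per subject but the sample size is in implants, so several denominators are shown: 40 subjects, 70 implants, 71 (one implant more), and 80 (40 patients × 2 implants on average). The event counts are illustrative.

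| n | Before removal | After removal | Shift (points) |
|---|---|---|---|
| 40 | 1/40: 13.16% | 0/40: 8.81% | 4.3 |
| 70 | 3/70: 12.02% | 2/70: 9.94% | 2.1 |
| 71 | 4/71: 13.80% | 3/71: 11.86% | 1.9 |
| 80 | 4/80: 12.31% | 3/80: 10.57% | 1.7 |

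The largest count with an upper limit below 12% is 0 for n = 29–44, 1 for 45–57, 2 for 58–70 and 3 for 71–82.

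**5. How often the count would sit one above that boundary**

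Binomial probability that the count before removals is exactly one more than the largest passing count, assuming independent units and the true rate shown:

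| True rate | n = 40, x = 1 | n = 70, x = 3 | n = 71, x = 4 | n = 80, x = 4 |
|---|---|---|---|---|
| 3% | 37% | 19% | 10% | 13% |
| 6% | 21% | 19% | 20% | 19% |
| 12% | 3.3% | 1.8% | 3.8% | 2.0% |

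For example, at 3% and n = 40: 40 × 0.03 × 0.97^39 = 0.366. These are chances of being in the sensitive position, not chances that a removal happens. The event must also be removable, and the subject must have no other qualifying complication, such as a hardware failure.

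**6. Denominator for off-label patients**

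Section 8.5 drops the off-label event but does not say whether the patient stays in the denominator. Section 8.6.1 requires treatment in line with the Instructions for Use, Section 8.14 discontinues patients found to breach a criterion, and Section 8.15 says that data of discontinued and replaced patients are still analysed. The numerical effect is small: 2/69 gives 10.08% against 9.94% for 2/70, and 0/39 gives 9.03% against 8.81% for 0/40.

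**The case against.** - **The rules help define a device endpoint.** A technique error or off-label use is arguably not a device effect, and the rule is written down in advance. This stands, and it is why the filtered rate can remain primary. It is no reason to leave the unfiltered rate unreported.
- **The Sponsor cannot remove a technique-error event alone.** The surgeon's finding and the Investigator's agreement are both needed. This limits misuse but does not make the review two-way. The off-label rule names no adjudicator.
- **The off-label rule should rarely apply**, because Section 8.6.1 already requires treatment in line with the Instructions for Use. This is fair, but the overlap leaves the denominator unclear.
- **Crossing 12% triggers nothing.** The analysis is descriptive and 12% is a planning target. True, but it is the upper end of the range to which the plan compares its result.
- **The probabilities overstate the risk.** If 10% to 30% of counted events were removable (an assumption; the documents give no figure), the chance at a 3% true rate of sitting one above the boundary with at least one removable event is about 4% to 11% at n = 40 (0.366 × 0.1 to 0.366 × 0.3). At n = 70 it is about 5% to 13% (0.192 × [1 − 0.9³] to 0.192 × [1 − 0.7³]). These are lower, but not negligible.
- **The n = 40 example mostly reflects sample size.** At 3%, the chance of at least one event is 1 − 0.97^40 = 70%, and any event puts the limit above 12%. This is correct, and the mismatch between subjects and implants is a separate matter. The n = 70 to 80 examples do not depend on it.
- **A before-removal rate does not recover events rated not related at the outset.** Also true: the fix shows what the removals did, not how accurate the first rating was.

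**Conclusion.** The concern holds and should be fixed. Followed exactly, Section 8.5 can lower the serious-event part of the primary safety numerator or leave it unchanged, but cannot raise it, and no section commits to showing the result before removals. This rests on the text and on no assumption about conduct.

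Near the boundary, one removal that changes a unit's status shifts the exact upper limit by about 1.7 to 4.3 points and can carry it across 12%. That size rests on illustrative counts at n = 40 to 80. The position probabilities also assume independent units and a given true rate. How often removals would occur cannot be known from the documents, nor can it be known whether the literature range was filtered in the same way. The endpoint is not invalid; the weakness is that readers may be unable to judge how far the result depends on removals. The denominator question is secondary, at about 0.1 to 0.2 points.

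**What to change.** In Sections 8.5 and 16, commit to reporting side by side, each with its denominator and exact 95% confidence interval:

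1. the primary endpoint on the Investigator's own causality rating (possibly or definitely related), before any removal;
2. the rate after technique-error and off-label removals.

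List every removed event with the reason. Which rate is labelled primary may stay as planned.

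As a secondary change, reconcile Section 8.5 with Sections 8.6.1, 8.14 and 8.15 so that a patient found to be off-label is handled the same way in numerator and denominator, whether or not an event occurred.

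The cost is some wording and one extra table. No new data are needed, because the events are already to be entered in the database. The drawback for the Sponsor is that the before-removal rate may look less favourable.
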